9.2 Sample Size and Randomization

We chose the largest feasible study size to obtain as precise estimates as possible of improvement in adolescent disability while ensuring adequate power for the treatment difference in the improvement in adolescent pain-related fear. This gave us a starting total sample size of 74 (37 in each arm). Based on pilot data, we expect roughly 19% attrition during treatment to a total of 60 and further attrition to 58 at end of follow-up.

Power calculations were first performed using the simplified approach of paired t-tests for the change from baseline to 3 and 6-months on those with 3 and 6-months data. For this approach, we used means and standard deviations of observed changes in pilot data. We then simulated data from our analytic model using the standard deviations at each time point and standard deviations of change to calculate correlation and hence the random effect and error variances. The mixed models simulation allowed us to use more data and yielded slightly higher power estimates.

Primary Outcome: In our primary power calculation, we assumed that the improvement in adolescent pain-related fear at 3 and 6-months would be 22.4 in GET Living and 5 in TPM, a difference of 17.4, with a standard deviation for change of 21. Under this scenario we will have power of 87% with 58 (29 in each arm) at end of study. Under more conservative assumptions, we still have power of 80% with only 52 at the end of study and a treatment difference of 16.6. With a smaller standard deviation of 18.9, we will have power of 80% with 50 at end of study and a treatment difference of 15.4.

Other Outcomes: For parent pain-related fear, our estimated treatment difference at 3 and 6-months is 13 with an estimated standard deviation for change of 8.5. This would give us power close to 100% for 58 at end of study and we would still have 90% power with a treatment difference of only 8 and only 50 left at end of study.

For adolescent disability, our estimated treatment effect at 3 and 6-months is 7 with a standard deviation for change of 11.2, yielding power based on the t-test of 65% assuming 58 at end of study. We also created 5000 simulated datasets using a mixed effects model with standard deviations of 11.2 for change and 12.6 at each time point and estimated power by the fraction of simulated datasets in which the treatment difference at 3 and 6-months was significant at level 0.05. This provided a slightly higher power estimate of 67% and an estimated power of 79% if the treatment difference is 8 (1 point larger than expected).

Treatment Assignment Procedures

After a 2-week pre-treatment baseline period, patients will be randomized to either GET Living or TPM and stratified on fear and disability scores (see **Table 6** for scoring criteria). A block

randomization strategy will be used with randomly generated blocks of 2 and 4 to assure near equal distributions across arms and minimize the probability of predicting the next assignment. A randomization spreadsheet with four strata will be created by the study biostatistician, [name] (please see **Table 5** in section 6.2.2 for fear and disability stratification).

Patients will be randomized by an un-blinded research coordinator or postdoctoral fellow. Those who are randomized to the TPM group can opt to participate in GET Living after their study assessments are complete (6.5 months after baseline). They will no longer be considered a participant of this study at that time.

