At treatment discharge for the GET Living intervention group and TPM treatment, participants will undergo a second biomechanical assessment and complete self-report questionnaires. After completion of the second assessment evaluation, participants are contacted for follow-up evaluation, which includes completion of the Daily Diary for a 7-day window and self-report questionnaires at each follow-up time point (3 and 6 months post-second assessment).

Interventions and Duration

The GET Living intervention will be compared to Typical Pain Management (TPM) provided at Stanford Children's Health. Each participant will be enrolled in the study for up to 40 weeks – Starting with the BAS visit, 2 weeks (on average) of a pre-treatment baseline period, approximately 6 weeks of active treatment, Discharge Assessment, and 3 and 6-month post-discharge follow-up. (See Figure 3 for a break-down of the study milestones and expected timeline.)

Sample Size and Population

An ideal recruitment site, Stanford houses a tertiary care pediatric pain management treating approximately 300 unique patients in the clinic each year. Patients who meet eligibility criteria will be informed of the study by their pain clinicians at clinic appointments and provided a study brochure. We aim to recruit a total of 74 participants into the study.

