1.1 Primary Objective

1a. To evaluate pain-related fear outcomes between GET Living and TPM. Hypotheses: Compared to TPM, the GET Living group will (1) have significantly less pain-related fear avoidance (adolescent, parent) at discharge, with continued gains at 3 and 6-month follow-up; Exploratory: (2) have fewer number of days to pain-related fear avoidance improvement via daily diaries.

1b. To evaluate disability and parent responses to pain outcomes between GET Living and TPM. Hypotheses: Compared to TPM, adolescents receiving GET Living will have (1) significantly less functional disability and protective parent responses at discharge, with continued gains at 3 and 6-month follow-up; Exploratory: (2) fewer number of days to achieve decreased functional disability and protective parent responses, assessed via daily diaries; (3) significantly better adolescent joint kinetics at discharge, assessed via motion analysis; and (4) demonstrate significantly greater increases in daily physical activity levels at discharge via Actigraphy. We will also examine treatment response correlates: age, pain, gender, diagnosis, and readiness to change.

2. To characterize feasibility and acceptability of GET Living compared to TPM to inform implementation of a large multi-site RCT. Hypotheses: GET Living participants will have (1) high treatment satisfaction ratings (mean score \geq 40 of 60; reflective of satisfied or very satisfied); Secondary: (2) \geq 80% sessions completed on-schedule, \leq 20% attrition rate, \geq 80% adolescent and parent daily diary adherence; Exploratory: (3) fewer health care costs at 3 and 6-month follow-up compared to TPM.

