Typical Pain Management (TPM) is a treatment intervention that is representative of current standards of care in a multidisciplinary pain clinic setting. We calculated historical PPMC treatment data for patients who met enrollment criteria (Mean sessions: Psychology=5 and PT=4). To ensure dose equivalency, we increased this to 6-Psychology/6-PT with 3 parent-only sessions. The CBT has been adapted from published manual for CBT treatment

of pediatric chronic pain and depressive symptoms ⁵² and the PT sessions are based on Guide to Physical Therapy Practice 3.0⁵¹.

Overview. The protocol consists of approximately 12 sessions, 1-hour each, delivered twice a week, on average for 6 weeks. Patient and parent will complete daily diaries and patients will wear the Actigraph throughout the duration of treatment. Sessions will alternate between psychological CBT sessions and Physical Therapy sessions, as outlined in Table 2 below. 3 Parent-only CBT sessions with the pain psychologist will be included to address parental coping skills.

Cognitive Behavioral Therapy (CBT). CBT will consist of 6 patient sessions and 3 parent-only sessions with a licensed pain psychologist focused on biopsychosocial model education, goal setting, coping skills training, and cognitive restructuring. The final CBT sessions with the psychologist will focus on relapse prevention, long term goals, reviewing of accomplishments during treatment.

Physical Therapy (PT). PT will consist of 6 sessions with a licensed physical therapist based on Guide to Physical Therapy Practice 3.0⁵¹ consisting of 1) therapeutic exercise, 2) balance and proprioception, 3) strength training, 4) use of modalities (e.g., heat/cold pack).

Discharge will consist of a second biomechanical motion analysis (**[name]**; Motion and Sports Performance Laboratory at SCH), and exit interview, and self-report questionnaires completed by patient and parent.

Follow-up will occur 3 and 6-months post-discharge assessment. During the follow-up period, patients and parents will be asked to complete 7-days of daily diaries and complete self-report questionnaires.

Table 3. Typical Pain Management Sessions

Session	Topic	Adolescent Content	Parent Content
1	Rapport Building, History	Build rapport; obtain patient history. Discuss goals for treatment.	Joint Session: Same content
2	PT Session 1	Adolescent in Physical Therapy	N/A

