Aim 1 Analysis Plan. GET Living vs. TPM. Linear mixed effects models will be used to compare GET Living to TPM. The outcome of interest for H_{1a} will be FOPQ-C and PFOPOQ total scores. For H_{1b}, outcomes are FDI and ARCS-Protect scores. Exploratory endpoints. Daily Diary (DD): We will use a randomization test (<https://tamalkd.shinyapps.io/scda/>)⁵³ to assess the difference between baseline (BAS) to discharge (END) and BAS to 3 and 6-month follow-up (FU)^{21,54}. We will also examine at what point during treatment significant improvements occur using delayed effect lags (one effect equals 1 day) until p-value 0.05 is reached. Actigraphy: Actilife software will be used to extract data and calculate mean and peak daily activity. Published data reduction methods will be used⁴³. We will model physical activity (mean, peak) at two time points using mixed 2 (time) x 2 (group) ANOVAs. Rate of change in physical activity from BAS to END will also be examined using DD method. Biomechanical assessment: Full body joint kinematic (motion) and kinetic (force) data will be collected with a 20-camera Vicon system (Centennial, CO, USA) with 5 integrated force plates (Bertec; AMTI). Markers will be placed on each participant according to the 3D Plug In Gait model (Vicon) with data recorded and processed in Nexus 2.6.1. Participants will walk, complete the Star excursion balance test and drop jump task^{37,41}. Biomechanical variables (stride length; peak hip and knee extensor moments; peak ankle plantarflexor moment; Star excursion balance score) will be extracted using Event Analyser (Vicon) for error free data reduction. We will model biomechanical variables using mixed 2 (time) x 2 (group) ANOVAs. We will also examine treatment response correlates: age, pain, gender, diagnosis, and readiness to change.

Aim 2: To characterize feasibility of GET Living to inform implementation of a large multi-site RCT.

Hypotheses: GET Living participants will have (1) high treatment satisfaction ratings (mean score ≥ 40 of 60; reflective of satisfied or very satisfied); *Secondary:* (2) $\geq 80\%$ sessions completed on-schedule, $\leq 20\%$ attrition rate, $\geq 80\%$ adolescent and parent daily diary adherence; *Exploratory:* (3) fewer health care costs at 3 and 6-month follow-up compared to TPM.

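### Section 9.2 dates TPM crossover about 4 to 6 weeks before the 6-month assessment it should follow; separately, sections 3 and 5.1 give different GET Living windows

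*Combined protocol and SAP*

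**What the plan says.** Section 9.2 (Treatment Assignment Procedures) lets families randomised to TPM take up the experimental treatment later: they "can opt to participate in GET Living after their study assessments are complete (6.5 months after baseline". It adds: "They will no longer be considered a participant of this study at that time".

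The length of TPM and the anchor for follow-up are in section 5.1. TPM is "approximately 12 sessions, 1-hour each, delivered twice a week, on average for 6 weeks", and "Follow-up will occur 3 and 6-months post-discharge assessment". The précis (Design and Outcomes) uses the same anchor, "3 and 6 months post-second assessment". The précis (Interventions and Duration) puts a pre-treatment period averaging 2 weeks after the baseline visit, then about 6 weeks of treatment, and caps enrolment at 40 weeks.

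The 6-month visit belongs to the primary hypothesis. Aim 1a in section 1.1 expects "significantly less pain-related fear avoidance (adolescent, parent) at discharge, with continued gains at 3 and 6-month follow-up".

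For GET Living, section 3 (Treatment Conditions) describes twelve 50-minute sessions, twice weekly, over at most 12 weeks. Section 5.1 describes twelve 1-hour sessions, twice weekly, over at most 6 weeks.

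**The concern.** The crossover sentence gives staff a condition (assessments finished) and a calendar date, and the two disagree. Follow-up is counted from discharge, so a date of 6.5 months after baseline has to leave room for the baseline period, the treatment and a further 6 months. It does not.

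If someone books crossovers by the date, a TPM family that opts in ceases to be a participant before its 6-month fear assessment. If that family were assessed anyway, its TPM score would be taken during GET Living. Section 9.3 does not separate intention-to-treat from per-protocol populations, and the plan gives no rule for either case. Any such loss falls on the TPM arm alone. It may also be selective, because families who opt in may be those still in need.

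The second inconsistency is independent of the first. Two sections describe the same GET Living course with different session lengths and different maximum durations, so a therapist or fidelity rater cannot tell which applies.

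**Working it through.** **Inputs.** Baseline period: 14 days on average (précis; section 3). TPM: 42 days on average (section 5.1). Last assessment: 6 months after discharge (section 5.1; précis). Stated crossover date: 6.5 months (section 9.2). One month is taken as 30.44 days, so 6 months = 182.6 days and 6.5 months = 197.8 days = 28.3 weeks.

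**1. Can the stated date be reproduced?** Time to last assessment = baseline period + treatment + 6 months.
- From the baseline visit: 14 + 42 + 182.6 = 238.6 days = 34.1 weeks = 7.8 months. Gap: 238.6 − 197.8 = 40.8 days = 5.8 weeks.
- From randomisation, at the end of the baseline period: 42 + 182.6 = 224.6 days = 32.1 weeks. Gap: 224.6 − 197.8 = 26.8 days = 3.8 weeks.
- Taking 6 months as 26 weeks changes the gaps to 5.7 and 3.7 weeks. Waiting for the 7-day follow-up diary adds 1 week to each.

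Neither starting point reproduces 6.5 months.

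**2. What treatment length would make the date right?** From the baseline visit: 197.8 − 14 − 182.6 = 1.2 days. From randomisation: 197.8 − 182.6 = 15.2 days. Twelve sessions at two a week span 11 × 3.5 = 38.5 days, so neither is possible under the planned schedule.

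**3. Which visits are exposed?** The 3-month assessment falls at 14 + 42 + 91.3 = 147.3 days = 21.0 weeks after the baseline visit, 7.2 weeks before the stated date. Only the 6-month visit is exposed.

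**4. Is power at stake?** The plan states: "Under this scenario we will have power of 87% with 58 (29 in each arm) at end of study". A two-sample t-test with difference 17.4, SD 21 and two-sided alpha 0.05 gives 0.873 at 29 v 29, which agrees. If TPM families are removed from the 6-month visit, power is 0.809 at 29 v 21 and 0.797 at 29 v 20, so it first drops below 80% when 9 of 29 leave. The documents give no expected number of early crossovers.

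**5. Which GET Living window fits the other figures?**
- 2 + 12 + 26 = 40 weeks, exactly the enrolment ceiling. With a 6-week maximum the total is 2 + 6 + 26 = 34.
- Mean treatment time for pilot completers was 64 days (section 2.2) = 9.1 weeks, longer than 6 weeks and shorter than 12.
- The ceiling leaves 280 − 182.6 = 97.4 days = 13.9 weeks for baseline plus treatment. A 12-week course uses 84 days and leaves 13.4 days for the baseline period (14 if 6 months is 26 weeks). Since that period is randomised with a mean of 2 weeks, a family with a longer one could not use all 12 weeks within the ceiling.

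**The case against.** The strongest reply is that the operative rule is the completion condition and the date is only a gloss on it. The schedule in section 6.1 and the follow-up text elsewhere all include a 6-month assessment, and the follow-up text counts it from discharge. To lose that visit, staff would have to overlook both the condition and the schedule. This stands, and it is why the point is minor. It does not make the date correct: the sentence governs when control families may move to the experimental treatment, and a wrong number there serves no purpose.

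A reader might infer that the drafters forgot treatment time, because 2 weeks plus 6 months comes to 28.1 weeks, close to 28.3. The documents do not say so. A wrong anchor word explains the figure equally well: 6 months after discharge plus the 7-day diary is (182.6 + 7) / 30.44 = 6.2 months, so 6.5 months after discharge would have been workable. The error is established; its cause is not.

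A reader might also infer that the 6- versus 12-week conflict undermines the Aim 2 target of at least 80% of sessions on schedule. Nothing in sections 1.1, 9.1 or 9.5.5 or in Table 6 ties that criterion to the overall window. It could refer to booked appointments, or to the twice-weekly cadence that both sections share. The criterion is undefined, which is a different matter.

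Finally, the two durations can largely be reconciled. Twelve sessions at two a week is nominally 6 weeks, and 12 weeks can be read as an outer limit. On that reading the phrase to correct is the 6-week maximum in section 5.1, not the text of section 3.

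**Conclusion.** Both inconsistencies are present in the current text, and both are minor. The crossover date is about 4 to 6 weeks too early (3.8 weeks from randomisation, 5.8 from the baseline visit), assuming the average 2-week baseline and the average 6-week TPM course. A family with longer treatment would have a larger gap.

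The consequence is conditional. If the completion condition is followed, no data are affected. If the date is followed, the 6-month fear assessment could be lost or contaminated in the TPM arm only, while the discharge and 3-month comparisons stay intact. The documents do not support saying that this loss will occur, or how large it would be: the number of early crossovers could be anything from none to all 29 TPM families expected at follow-up. Power is not the main issue. The plan states that "Linear mixed effects models will be used to compare GET Living to TPM", and such models keep the earlier visits of families who leave. What remains is a one-sided and possibly selective loss that the plan can exclude at almost no cost.

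The GET Living conflict (50 minutes and at most 12 weeks, against 1 hour and at most 6) needs one statement used in both sections. No effect on a listed outcome can be shown from the documents.

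**What to change.** Section 9.2: delete the 6.5-month parenthesis. State that a TPM family may start GET Living only once its own 6-month post-discharge assessment is recorded, nominally about 34 weeks after the baseline visit. Report the number and timing of any crossovers that happen earlier.

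Sections 3 and 5.1: give one session length and one window in both. The simplest repair is to replace the 6-week maximum in section 5.1 with a nominal 6 weeks and a single outer limit, and to use the same words in section 3. To respect the 40-week ceiling, that limit should be no more than 13.9 weeks minus the longest baseline period in the randomisation scheme. If the full 12 weeks is wanted for families with a baseline longer than about 2 weeks, raise the ceiling instead.

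The cost is wording only. Visits, sample size and significance levels do not change. TPM families who want GET Living wait about 4 to 6 weeks beyond the date now printed, which the completion condition already requires.

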9.3 Definition of Populations

We do not plan to differentiate ITT and per protocol populations for the analyses.

9.4 Interim Analyses and Stopping Rules

When we reach 50% of our planned sample of treatment completers, we will conduct an interim analysis. The intent of this interim analysis is to implement stopping rules for either overwhelming efficacy or futility.

In order to maintain power at full planned enrollment (in the case that the interim analysis does not stop the study) without adding subjects while also accounting for the additional look at the data, we will use O'Brien-Fleming significance levels (0.0054 for the interim analysis and 0.0492 for the final analysis). For futility, we propose a conditional power approach where we will stop for futility if the conditional power is below 10%. Adding a futility rule for stopping does not require further reduction of significance levels since it decreases the chance of a type I error.

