9.6 Data Analyses

Our statistician, [name], will conduct analyses. Linear mixed effects models will be used for Aim 1. We chose the largest feasible study size to obtain as precise estimates as possible of treatment difference in our primary outcome, adolescent pain-related fear. With a starting sample of 74 (37/37), we expect 58 at follow-up (18% discharge attrition, 5% at 3 and 6-month follow-up). Using GET Living pilot data (see Table 2), we used a mixed model simulation using the standard deviations at each time point and standard deviations of change to calculate correlation and hence the random effect and error variances. In our primary power calculation, we assumed that the improvement in adolescent pain-related fear at 3 and 6-months would be 22.4 in GET Living and 5 in TPM¹⁹, a difference of 17.4, with a standard deviation for change of 21. Under this scenario we will have 87% power with 58 (29 in each arm) at study end. Under more conservative assumptions, we still have power of 80% with only 52 at the end of study and a treatment difference

of 16.6. With a smaller standard deviation of 18.9, we will have power of 80% with 50 at end of study and a treatment difference of 15.4.

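### The O'Brien-Fleming levels in section 9.4 (0.0054 and 0.0492) are slightly too large: at half information, with non-binding futility, they spend 5.13% two-sided; 0.0052 and 0.0480 would spend 5%

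*Combined protocol and SAP*

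**What the plan says.** Section 9.4 times the look by completers: "When we reach 50% of our planned sample of treatment completers, we will conduct an interim analysis". It allows stopping for efficacy or futility and adopts O'Brien-Fleming "significance levels (0.0054 for the interim analysis and 0.0492 for the final analysis". It offers these as the way to keep power at full enrolment "while also accounting for the additional look at the data". For futility it says "we will stop for futility if the conditional power is below 10" percent. It adds that this rule calls for no further lowering of the levels, because it can only reduce the type I error.

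Section 9.4 gives no overall significance level and does not say whether the tests are one- or two-sided. It does not say whether the futility stop is binding, or which effect enters the conditional power. The nearest statement of a level is in section 9.2, where the disability simulation counts data sets in which "the treatment difference at 3 and 6-months was significant at level 0.05". The same section gives the main power figure for adolescent fear: "Under this scenario we will have power of 87% with 58 (29 in each arm) at end of study".

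**The concern.** O'Brien-Fleming levels for a given number of looks, timing and overall alpha are fixed numbers, so they can be checked. For two equally spaced looks at two-sided 5%, the stated pair is not that boundary. Both levels are a little larger than they should be, so together they spend a little more than 5%. They are the only thresholds in the plan for an efficacy stop and for the final claim. A p-value falling between a stated level and the exact level would be called significant under a rule that does not quite hold 5%.

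**Working it through.** **Inputs.** Levels 0.0054 and 0.0492, and one look at 50% of completers (section 9.4). Difference 17.4, SD of change 21, 29 per arm, stated power 87% (section 9.2). Three assumptions: overall two-sided 5%; information proportional to completers, so a fraction t = 0.5; futility non-binding.

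**Step 1: support for two-sided 5%.** The noncentrality of a two-sample t-test is 17.4 / (21 × √(2/29)) = 3.155 on 56 df. Power is 87.3% at two-sided 0.05 and 92.9% at one-sided 0.05. Only the two-sided test reproduces the stated 87%.

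**Step 2: shape of the stated pair.** The two-sided normal quantiles are z₁ = 2.782 for 0.0054 and z₂ = 1.967 for 0.0492. Their ratio is 2.7822 / 1.9669 = 1.4145, which is √2 to three decimals. An O'Brien-Fleming boundary for two equal looks has z₁ = C√2 and z₂ = C, so the pair is that boundary with C = 1.967.

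**Step 3: what the pair spends.** Under the null the two statistics have correlation √t = √0.5. By numerical integration, P(|Z₁| > 2.7822 or |Z₂| > 1.9669) = 0.0513; a simulation of 20 million draws also gives 0.0513. The excess is 5.13% − 5.00% = 0.13 percentage points.

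**Step 4: the exact boundary.** Solving P(|Z₁| > C√2 or |Z₂| > C) = 0.05 gives C = 1.9774, with levels 0.00517 and 0.04799. Rounded to 0.0052 and 0.0480, they spend 5.002%. If 0.0054 is kept at the interim, the final level that holds 5% is 0.0479.

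**Step 5: could another standard construction explain the pair?** None of those tried does.

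| Construction at half information | Interim | Final |
|---|---|---|
| Stated in section 9.4 | 0.0054 | 0.0492 |
| O'Brien-Fleming, two-sided 5% | 0.0052 | 0.0480 |
| O'Brien-Fleming-type spending, two-sided 5% | 0.0056 | 0.0478 |
| O'Brien-Fleming-type spending, 2.5% per side | 0.0031 | 0.0490 |
| O'Brien-Fleming, one-sided 5% | 0.0088 | 0.0467 |

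**Step 6: sensitivity to timing.** Section 9.2 expects 60 completers ("we expect roughly 19% attrition during treatment to a total of 60"), so half is 30. If half of the planned sample were read instead as 37 of 74, the fraction would be 37/60 = 0.617.

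| Information fraction | 0.40 | 0.50 | 0.617 | 0.70 | 0.80 |
|---|---|---|---|---|---|
| Spent by 0.0054/0.0492 | 5.20% | 5.13% | 5.05% | 5.00% | 4.95% |

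The fractions 0.40, 0.70 and 0.80 are assumed, to show the range.

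**Step 7: sensitivity to futility.** If the 10% conditional-power stop is binding at half information, the stated pair totals 4.6% (current trend, either direction), 2.6% (current trend, one direction) or 3.1% (design effect in the planned direction).

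**The case against.** The strongest reply is that futility returns the alpha. Section 9.4 says the trial will stop, with no discretionary wording, and notes that this lowers the type I error. On the binding readings above, the total is below 5%. This stands as a limit on the point: the excess exists only if futility is non-binding. It does not justify the two numbers. Section 9.4 presents them as the adjustment for the extra look and says only that futility needs no further reduction; it does not say the levels were relaxed because of futility. Nor does it say that the stop is binding or how conditional power is computed, so the credit cannot be fixed.

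A second reply is that section 9.4 names no overall level, and that the 0.05 in section 9.2 belongs to a simulation for disability, the secondary outcome. That is correct; two-sided 5% is an inference, though the power figures support it.

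A third is that the amount is trivial in a trial the protocol calls exploratory. That largely stands, and it is why this is a minor correction.

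A reader might go further and infer that the trial fails to control its type I error, or that the boundary must be replaced by a spending function. The documents support neither. The first ignores the conditions just given and the range of information fractions in which the excess shrinks or vanishes. The second is a design preference with a price: the version with 2.5% per side cuts the chance of an early efficacy stop under the design effect from 29% to 23% at half information. Correcting the numbers does not require it.

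**Conclusion.** The stated levels are numerically wrong for the boundary they are named after. Assuming an overall two-sided 5%, half information and non-binding futility, they spend 5.13%. The error lies in the constant, not in the shape. In practice only a p-value of 0.0052 to 0.0054 at the interim, or of 0.0480 to 0.0492 at the end, would be judged differently. The point does not show that the trial's overall error exceeds 5% on every reading of section 9.4, and it casts no doubt on the design or the sample size.

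**What to change.** In section 9.4, replace the two levels with 0.0052 (interim) and 0.0480 (final). Alternatively, keep 0.0054 and change only the final level to 0.0479, which also holds 5% at half information. Add one sentence saying that the levels hold an overall two-sided 5% for one look at half information, with futility treated as non-binding for alpha.

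The cost is a change of wording. At 29 per arm, final-look power by t-test goes from 87.1% at 0.0492 to 86.9% at 0.0480 or 0.0479, so the stated 87% stands. In the two conservative scenarios of section 9.2, the same calculation gives 79.6% to 79.3% (26 per arm, difference 16.6, SD 21) and 80.4% to 80.1% (25 per arm, difference 15.4, SD 18.9). The first rounds to 79% instead of 80% by t-test, although section 9.2 reports slightly higher power from its mixed-model simulation. Sample size and the interim trigger do not change.
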